#### 8.4. Time-to Onset for Adverse Events of Special Interest

Time to onset of AESI PTs grouped in special categories since start of the study treatment will be summarized for events observed amongst subjects who experienced at least one AESI.

Descriptive statistics will be presented by any grade and grade 3-5 for each treatment arm for summaries shown in [Table 15](#). See algorithm details in [Appendix G](#).

#### 8.5. Time-to Resolution of Adverse Events of Special Interest

Time to resolution for AESIs will be summarized by any grade and grade 3-5 by treatment arms for summaries shown in [Table 15](#) amongst subjects who experienced at least one AESI.

Analysis of time-to resolution will be by Kaplan-Meier method as described in [Section 7.1.5](#).

Number, percentage, median and 95% CI of the select PTs will be reported. See algorithm details in [Appendix H](#).

#### 8.6. Challenge/Re-Challenge for Select Adverse Events of Special Interest

Subjects who experience at least one AESI or liver test abnormalities as characterized by ALT or AST and were re-challenged with either the study treatment, cabozantinib, nivolumab or

ipilimumab after its resolution will be summarized by treatment arm for summaries shown in [Table 15](#).

## 8.7. Laboratory Assessments

### 8.7.1. Variables

The following treatment-emergent laboratory abnormalities will be summarized ([Table 17](#)). A treatment emergent laboratory abnormality is defined as any laboratory abnormality with an onset date on or after the date of the first dose of study drug.

**Table 17: Summary of Laboratory Tests**

Category	Abnormality	SDTM LBTESTCD	Grading System
Hematology	WBC decreased	WBC	CTCAE
	ANC decreased	NEUT	CTCAE
	Lymphocytes increased Lymphocytes decreased	LYM	CTCAE
	Platelets decreased	PLAT	CTCAE
	Hemoglobin increased Hemoglobin decreased	HGB	CTCAE
Serum chemistry	Albumin decreased	ALB	CTCAE
	ALP increased	ALP	CTCAE
	Amylase increased	AMYLASE	CTCAE
	ALT increased	ALT	CTCAE
	AST increased	AST	CTCAE
	Calcium, corr increased Calcium, corr decreased	CACORR	CTCAE
	Creatinine increased	CREAT	CTCAE
	GGT increased	GGT	CTCAE
	Glucose increased Glucose decreased	GLUC	CTCAE
	LDH increased	LDH	Sponsor
	Lipase increased	LIPASE	CTCAE
	Magnesium increased Magnesium decreased	MG	CTCAE
	Phosphate decrease	PHOS	CTCAE
	Potassium increased Potassium decreased	K	CTCAE
	Sodium increased Sodium decreased	NA	CTCAE

Category	Abnormality	SDTM LBTESTCD	Grading System
	Total bilirubin increased	BILI	CTCAE
Urine chemistry	UPCR increased	PROTCRT	Sponsor
Endocrinology 	Thyroid Stimulating Hormone increased Thyroid Stimulating Hormone decreased	TSH	HLN

 TSH is held in the SDTM “chemistry” laboratory category; will use HLN = high, low, normal classification based on normal range

Sponsor-defined grades are to be applied to the following analytes:

**LDH:**

- Grade 1 if  $>$  ULN to  $\leq 2 \times$  ULN
- Grade 2 if  $> 2 \times$  ULN to  $\leq 3 \times$  ULN
- Grade 3 if  $> 3 \times$  ULN

**UPCR:**

- Grade 1 if  $\geq 17.0$  to  $\leq 121.0$  mg/mmol ( $\geq 0.15$  to  $\leq 1.0$  mg/mg)
- Grade 2 if  $> 121.0$  to  $\leq 396.0$  mg/mmol ( $> 1.0$  to  $< 3.5$  mg/mg)
- Grade 3 if  $> 396.0$  mg/mmol ( $> 3.5$  mg/mg)

### 8.7.2. Analysis

All laboratory data parameters and visits will include flags for values above or below laboratory reference ranges. Toxicity grades will be assigned programmatically by applying the CTCAE v5.0 guidelines. Only results with assessment dates through the end of the standard safety observation period (see [Section 4.5](#)) will be tabulated in summary tables.

Laboratory summaries will be presented in SI units. Continuous laboratory test results will be summarized by treatment group using descriptive statistics for actual values and for changes from baseline by scheduled visit. Plots showing mean and standard error at each scheduled visit (with visits shown on x-axis) may also be presented for some laboratory parameters. For test results which are below or above the quantification level, the imputed values as described in [Appendix C](#) will be used for deriving the grade and then summarized.

Tables summarizing baseline laboratory values and the incidence of laboratory abnormalities by baseline and maximum post-baseline CTCAE grade over all records will be presented. In addition, the following summaries will also be presented:

A. Liver function abnormalities will be assessed as follows:

- Shift from baseline based on normal ranges

- Summaries of subjects meeting Hy's Law laboratory screening criteria as shown below:
  - $> 3 \times \text{ULN}$  (ALT or AST),  $> 2 \times \text{ULN}$  Total Bilirubin, and  $< 2 \times \text{ULN}$  ALP
  - $> 3 \times \text{ULN}$  (ALT or AST),  $> 2 \times \text{ULN}$  Total Bilirubin, and  $\geq 2 \times \text{ULN}$  ALP
  - $> 3 \times \text{ULN}$  (ALT or AST),  $> 2 \times \text{ULN}$  Total Bilirubin

B. For renal failure surveillance, a summary of subjects meeting renal failure laboratory screening criteria as shown below will be provided:

- Serum creatinine  $\geq 3.0 \times \text{ULN}$  and  $\geq 2.0 \times$  baseline value or
- Estimated Glomerular Filtration Rate (eGFR)  $\leq 50\%$  of the baseline value or
- eGFR  $< 30 \text{ mL/min/1.73 m}^2$  and  $\geq 25\%$  reduction from the baseline value

$$\text{eGFR} = 186 \times (\text{Creatinine in mmol per L} / 88.4)^{-1.154} \times (\text{Age})^{-0.203} \times (0.742 \text{ if female}) \times (1.210 \text{ if black}) \quad [\text{from website: } \text{https://ukidney.com/nephrology-resources/egfr-calculator}]$$

C. Categorical summaries for baseline status for TSH and Free T4 will be presented. In addition, categorical summaries for post-baseline TSH and Free T4 status among subjects with TSH and Free T4 in the normal range at baseline will also be presented.

For descriptive summaries of change from baseline in continuous laboratory variables and analyses of shift in grade from baseline or worst grade after baseline, all available results will be considered regardless of whether from the central or local lab. See [Table 18](#) for the list of laboratory tests which will be included in the analysis.

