**Table 5-3: Estimation of the Creatinine Clearance by Cockcroft and Gault**

Serum creatinine in conventional units (mg/dL)
• Males: $(140 - \text{age}) \times \text{weight (kg)} / (\text{serum creatinine} \times 72)$
• Females: $[(140 - \text{age}) \times \text{weight (kg)} / (\text{serum creatinine} \times 72)] \times 0.85$
Serum creatinine in SI units (μmol/L)
• Males: $[(140 - \text{age}) \times \text{weight (kg)} / (\text{serum creatinine})] \times 1.23$
• Females: $[(140 - \text{age}) \times \text{weight (kg)} / (\text{serum creatinine})] \times 1.04$

Abnormalities in any clinical laboratory test (including tests not required per protocol) that lead to a change in subject management (eg, dose interrupted or reduced, treatment discontinued, requirement for additional medication or monitoring) are considered clinically significant for the purposes of this study and should be reported as AEs. If laboratory values constitute part of an event that meets seriousness criteria, the event (with associated laboratory values) needs to be reported as an SAE (see [Section 8.2](#)).

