**Table 6-10: Adverse Event Criteria for Dose Delay, Resumption, and Discontinuation of Nivolumab and Ipilimumab**

Drug-Related AEs per CTCAE V5	Severity	Action Taken	Clarifications, Exceptions, and Resume Criteria
Gastrointestinal			
Colitis or Diarrhea	Grade 2	Delay dose.	Dosing may resume when AE resolves to baseline.
	Grade 3	Nivolumab monotherapy: Delay dose.	Dosing may resume when AE resolves to baseline.
		When administered with ipilimumab: Permanently discontinue Ipilimumab.	Nivolumab monotherapy may be resumed when AE resolves to baseline. If Grade 3 diarrhea or colitis recurs while on nivolumab monotherapy, permanently discontinue.
	Grade 4	Permanently discontinue.	-
Renal			
Serum Creatinine Increased	Grade 2 or 3	Delay dose.	Dosing may resume when AE resolves to Grade $\leq$ 1 or baseline value.
	Grade 4	Permanently discontinue.	-
Pulmonary			
Pneumonitis	Grade 2	Delay dose.	Dosing may resume after pneumonitis has resolved to $\leq$ Grade 1.
	Grade 3 or 4	Permanently discontinue.	-

CONFIDENTIAL

Protocol XL184-313 Protocol Amendment 3.0  
Page 104 of 193

Drug-Related AEs per CTCAE V5	Severity	Action Taken	Clarifications, Exceptions, and Resume Criteria
Endocrinopathy			

 
May resume treatment if drug-related endocrinopathies adequately controlled with only physiologic hormone replacement.
 
			
Adrenal Insufficiency	Grade 2 adrenal insufficiency	Delay dose.	Dosing may resume after adequately controlled with hormone replacement.
	Grade 3 or 4 adrenal insufficiency or adrenal crisis	Delay dose or permanently discontinue.	Mandatory discussion with and approval from the Medical Monitor needed prior to resuming therapy. If adrenal insufficiency resolves or is adequately controlled with physiologic hormone replacement, participant may not require discontinuation of study drug.
Hyperglycemia	Hyperglycemia requiring initiation or change in daily management (Grade 2 or 3)	Delay dose.	Dosing may resume if hyperglycemia resolves to Grade $\leq 1$ or baseline value, or is adequately controlled with glucose-controlling agents.
	Grade 4	Delay dose or permanently discontinue.	Mandatory discussion with and approval from the Medical Monitor needed prior to resuming therapy. If hyperglycemia resolves, or is adequately controlled with glucose-controlling agents, participant may not require discontinuation of study drug.

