### **8.1.2      Laboratory Abnormalities**

All laboratory data required by this protocol and any other clinical investigations will be reviewed by the Investigator. Any abnormal value that leads to a change in subject management (eg, dose reduction, delay, or study drug discontinuation, or requirement for additional medication or monitoring) or that is considered to be of clinical significance by the Investigator will be reported as an AE or SAE as appropriate, unless this value is consistent with the subject’s present disease state or is consistent with values obtained prior to entry into the study.

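### High glucose is graded by program from laboratory values under CTCAE v5.0, but the only graded wording in the documents describes Grade 2 or 3 by a management change, so those cells would probably be empty whatever the values are

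*SAP*

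**What the plan says.** SAP Table 17 lists "Glucose increased Glucose decreased" in a single serum-chemistry row whose grading system is CTCAE. SAP 8.7.2 gives the rule: "Toxicity grades will be assigned programmatically by applying the CTCAE v5.0 guidelines". On the input, it says that results outside the quantification range are imputed by Appendix C, and that the imputed values "will be used for deriving the grade and then summarized". It names no medication or management data as an input to the grade.

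Three analytes are treated differently. Under the line "Sponsor-defined grades are to be applied to the following analytes", the SAP writes numeric limits for LDH and UPCR. The Table 17 footnote says that TSH "will use HLN = high, low, normal classification based on normal range". Glucose has neither arrangement.

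The only graded description of hyperglycemia in the two documents is in protocol Table 6-10, whose first column is labelled as drug-related AEs under CTCAE version 5. The severity entry reads "Hyperglycemia requiring initiation or change in daily management (Grade 2 or 3"). It gives no glucose limit. Grade 4 has its own line without a criterion.

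The protocol routes management changes to the adverse event record. Section 5.7.5 says that laboratory abnormalities of this kind "are considered clinically significant for the purposes of this study and should be reported as AEs". Section 8.1.2 opens a similar instruction with "Any abnormal value that leads to a change in subject management".

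**The concern.** A program that reads only laboratory results cannot know whether a patient started or changed glucose-lowering treatment. If that change is what makes an event Grade 2 or 3, the program has nothing from which to assign those grades. The cells would hold zeros that say nothing about the patients.

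The zero that matters is the one under Grade 3. The protocol names hyperglycemia among the laboratory-related events seen with cabozantinib (6.6.2.1) and among the endocrinopathies caused by checkpoint inhibitors (6.6.3.1). A reader comparing the arms could take an empty Grade 3 column as evidence that neither regimen raised glucose severely. No efficacy result, error rate or sample size is touched.

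**Working it through.** The plan states no figure on this point, so the check sets the texts side by side and then counts how far the problem reaches.

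**1. What the program can see.** SAP 8.7.2 grades by program and describes only laboratory results, central or local, as input. The sentence about deriving the grade concerns out-of-range results, so it does not strictly exclude other inputs. But no other input is named anywhere in 8.7.

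**2. What Grade 2 or 3 requires.** Two readings of the Table 6-10 entry are possible.
- *Label reading:* the management description is the criterion, and the bracketed grades name it.
- *Qualifier reading:* grades come from elsewhere, and the phrase only limits which Grade 2 or 3 events call for a dose delay.

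**3. Which reading fits the table better.**
- Where Table 6-10 restricts a grade, it builds the grade into the phrase and qualifies it. The rash row takes Grade 2 above a body-surface threshold. The hypophysitis row takes Grades 1 to 3 with symptoms and supporting tests. The pancreatitis row takes Grade 3 with symptoms.
- The hyperglycemia entry does the reverse: description first, grades in brackets after it.
- The serum creatinine row gives Grades 2 and 3 with no description at all.

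This pattern favors the label reading. It is evidence from layout, not a definition.

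**4. Consequence on the label reading.** Grade 2 or 3 needs a management change; the program sees only values; so no glucose value, however high, yields Grade 2 or 3. Nothing follows for Grade 1 or Grade 4, because the documents give no criterion for either.

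**5. Whether another CTCAE version could fill the cells.** SAP section 11 cites Version 5.0 but dates it to 28 May 2009 with a v4.03 note. The protocol reference list dates version 5.0 to 27 November 2017. A programmer could take numeric limits from another version, but the tables would then not follow the v5.0 rule in 8.7.2.

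**6. Reach.**
- Table 17 analytes: 5 hematology + 16 serum chemistry + 1 urine + 1 TSH = 23. Grading systems: 20 CTCAE + 2 sponsor + 1 high/low/normal = 23. The point concerns one direction of one of the 20.
- Table 18 has 8 summary types. Wholly grade-based for glucose: 2 (incidence by CTCAE grade, shift by CTCAE grade). Grade-based in the Grade 3-4 part of a 2% filter: 3. Unaffected: 8 − 2 − 3 = 3 (change from baseline, high/low/normal shift, sponsor-grade shift).
- In the three filtered tables, the 5% all-grade route still works if high values receive any grade.

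**The case against.** The strongest objection is that the deciding fact is not in the documents. Neither reproduces the CTCAE v5.0 definition of hyperglycemia, and Table 6-10 governs dose delay, not grading. The amylase and lipase entry shows that the table can attach a clinical condition to a grade that exists without it: it says that a Grade 3 enzyme rise without symptoms needs no delay. One phrase covering Grades 2 and 3 together also cannot separate them. This stands as a limit on certainty. It does not reverse the comparison in step 3, because the amylase and lipase entry also puts the grade inside the phrase.

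A second objection is that little is lost. A glucose value that changes management is an adverse event under protocol 5.7.5 and 8.1.2, and SAP Table 15 tabulates adverse events by grade. Diabetes mellitus is an event of special interest in protocol Table 8-1. Range flags and change from baseline remain, as does any high/low/normal shift table that covers glucose. Most of this stands, and it is why the point is minor. It is not complete: 8.1.2 exempts values consistent with the subject's present disease state or with values before entry, and protocol 4.3 admits subjects with type I diabetes. A value-based laboratory table does not depend on that judgment.

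A third objection is that SAP 4.8 lets operational clarifications go into an addendum. That is true, and it would be an acceptable place for the fix.

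A reader might infer more: that severe hyperglycemia would go unreported in this trial, or that the citation in section 11 shows grading under v4.03. The documents support neither. The adverse event route remains open, and SAP 8.1 and 8.7.2 both name v5.0.

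**Conclusion.** The point holds as a minor one. The SAP sends high glucose to a grading rule that, on the better-supported reading of protocol Table 6-10, laboratory values cannot satisfy at Grade 2 or 3. Those cells in the CTCAE-graded incidence and shift tables, and the Grade 3 part of the 2% filters, would then be empty whatever the glucose values are. If numeric limits from elsewhere fill them, the tables follow a rule that the SAP does not state.

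The conclusion rests on two assumptions: that the Table 6-10 entry reflects how v5.0 describes Grade 2 and 3, and that the program uses laboratory results only. Both are likely and neither is proven. If the entry is only a dose-delay qualifier, the cells need not be empty. No frequency of hyperglycemia can be projected from the documents, so the number of misclassified patients cannot be given.

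**What to change.** Split the glucose row in SAP Table 17 and leave the decrease under CTCAE. Move the increase to one of two value-based scales that the SAP already uses:

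- **Sponsor-defined cut-offs (preferred).** List numeric limits in SI units beside LDH and UPCR, report them in the existing sponsor-grade shift table of Table 18, and state whether sponsor Grade 3 counts in the Grade 3-4 filters. The limits are the sponsor's choice, since the documents give none.
- **High/low/normal**, as for TSH. This needs no cut-offs but gives up severity grading of high glucose in the laboratory tables.

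In either case, add a footnote such as: *Laboratory categories for high glucose are not CTCAE v5.0 grades; hyperglycemia by CTCAE grade is reported in the adverse event tables.* Correct the CTCAE citation in SAP section 11 in the same edit.

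The cost is one split row, a few lines of limits at most, a footnote and a corrected reference, with no new data. The downside is that laboratory glucose and adverse-event hyperglycemia will be on different scales in one report, which the footnote discloses.

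### The SAP's eGFR formula labels creatinine as mmol/L but divides by 88.4, the µmol/L factor; followed as written, eGFR is about 2,900 times too high and the below-30 renal-failure criterion can never be met

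*SAP*

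**What the plan says.** SAP section 8.7.2, item B, plans a summary of subjects who meet any one of three laboratory screening criteria for renal failure:

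1. serum creatinine at least 3.0 × ULN and at least 2.0 × the baseline value;
2. eGFR at or below 50% of the baseline value;
3. eGFR below 30 mL/min/1.73 m² together with at least a 25% reduction from baseline.

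It then defines eGFR as 186 × (creatinine / 88.4)^-1.154 × age^-0.203, multiplied by 0.742 if female and 1.210 if black. The creatinine term is labelled "Creatinine in mmol per L".

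The same section states "Laboratory summaries will be presented in SI units", but apart from the formula the SAP names no SI unit for serum creatinine. The protocol does: Table 5-3 gives a Cockcroft-Gault version headed "Serum creatinine in SI units", and the unit shown there is µmol/L.

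**The concern.** The constant 186 and the exponent -1.154 act on creatinine in mg/dL, so the division by 88.4 has to be the conversion to mg/dL. That conversion is right for µmol/L and wrong by a factor of 1,000 for mmol/L. Because the exponent is negative, a value 1,000 times too small gives an eGFR several thousand times too large.

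Criterion 3 is the only one of the three that compares eGFR with an absolute threshold, so it is the one that fails. Criterion 2 compares eGFR with its own baseline and gives the same answer in either unit. The planned output counts subjects meeting criteria, so the fault need not show in the table. Renal toxicity is of interest in this trial: nephritis is listed as an adverse event of special interest in Protocol Table 8-1.

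**Working it through.** **What 88.4 converts, from the protocol's own figures**

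- Protocol Table 5-3, males: the mg/dL form divides by 72 and the µmol/L form multiplies by 1.23, so 1 mg/dL = 72 × 1.23 = 88.6 µmol/L.
- Protocol Table 5-3, females: 72 × 1.04 / 0.85 = 88.1 µmol/L per mg/dL.
- Protocol inclusion criterion 8h: 1 mg/mg = 113.2 mg/mmol for the urine protein/creatinine ratio, so 1 mg/dL = 10 / 113.2 = 0.0883 mmol/L = 88.3 µmol/L.

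The SAP's 88.4 is therefore reproduced as the µmol/L factor. For mmol/L it would be 0.0884.

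**Size of the error**

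A given creatinine expressed in mmol/L is 1/1,000 of its value in µmol/L, so the computed eGFR is multiplied by 1000^1.154 = 2,897.

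**Worked values: man aged 60, race factor 1**

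| Creatinine (µmol/L) | eGFR with µmol/L | eGFR as written, mmol/L |
|---|---|---|
| 88.4 | 81.0 | 234,719 |
| 150 | 44.0 | 127,510 |
| 265.2 | 22.8 | 66,062 |
| 353.6 (4.0 mg/dL) | 16.4 | about 47,400 |
| 500 | 11.0 | 31,779 |
| 2,000 | 2.2 | 6,417 |

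**Creatinine needed for eGFR = 30**

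Solving 186 × (x / 88.4)^-1.154 × 60^-0.203 = 30 gives x = 209. That is 209 µmol/L (2.4 mg/dL) with the right unit, and 209 mmol/L (about 2,365 mg/dL) as written. Across the combinations of age (18 to 90), sex and race tried, the threshold as written ran from 150 to 305 mmol/L. No patient can reach it.

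**Which criteria still work**

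- Criterion 1 uses creatinine only and is unaffected.
- Criterion 2 is a ratio: creatinine going from 90 to 180 µmol/L gives an eGFR ratio of 0.449 in either unit.
- Criterion 1 adds nobody to criterion 2. Doubling creatinine cuts eGFR to 2^-1.154 = 0.449 of baseline, already below 50%. Age is recorded once, at consent (SAP section 5.3), and cancels.
- Criterion 3 is therefore the only one that can add subjects to criterion 2, and it is the one disabled.

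**Who is lost**

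These are subjects with a true eGFR below 30 after a fall of at least 25% but less than 50%. In creatinine terms the rise is from (1/0.75)^(1/1.154) = 1.28-fold to just under 2^(1/1.154) = 1.82-fold. Their baseline eGFR must be below 60, since a fall of less than 50% has to end below 30.

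Such subjects can be enrolled. Inclusion criterion 8g accepts a calculated clearance of at least 40 mL/min. By Table 5-3, a 60-year-old, 74-kg man with creatinine 180 µmol/L has clearance (140 − 60) × 74 × 1.23 / 180 = 40.5. If his creatinine rises to 240 µmol/L:

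- true eGFR goes from 35.7 to 25.6, a 28% fall, so criterion 3 should flag him;
- as written, his eGFR after the rise is 74,129, so criterion 3 does not;
- criterion 2 does not (ratio 0.717), nor does criterion 1 (240 / 180 = 1.33 times baseline).

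**The case against.** The arithmetic is not in dispute. Four points can be made against its weight.

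- **The result depends on what is fed in.** If the program supplies µmol/L, which is the protocol's SI unit for serum creatinine, every eGFR is correct and only the label is wrong. This stands as a condition on the consequence. It does not rescue the text, because a correct result would require the programmer to depart from the written specification.
- **It may be a character slip.** A micro sign rendered as the letter m cannot be ruled out from the text alone. The micro sign is intact in Protocol Table 5-3, but that is a separate file and the SAP text has no other micro sign for comparison. A look at the SAP page settles this.
- **Other criteria catch many of the same patients.** The man at 4.0 mg/dL would still be flagged by criterion 2 if his baseline was at or below 4.0 / 1.82 = 2.19 mg/dL. That example shows the size of the error, not a missed patient; the 180 to 240 µmol/L case shows the miss. The affected group is narrow, and the documents do not allow its size to be estimated.
- **Little rests on it.** No formal safety comparison is planned (SAP section 8), creatinine increases are graded separately by CTCAE (SAP Table 17), and absurd eGFR values might be noticed at the data review meeting (SAP section 10). This is right about importance, but a chance of later detection is no reason to leave a wrong formula in place.

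**Conclusion.** The concern holds. As written, the formula pairs mmol/L with the µmol/L divisor, overstates eGFR by a factor of 2,897 and makes criterion 3 unattainable. Nothing elsewhere in the SAP corrects the label.

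In practice, subjects whose true eGFR drops below 30 after a decline of at least 25% but less than 50% would be left out of the renal failure count; criteria 1 and 2 keep working. This consequence assumes that the formula is programmed literally and that the label is what the SAP page shows. Efficacy analyses, alpha, sample size and stopping rules are not touched. It is a clear error in one descriptive safety summary and should be corrected before that table is produced.

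**What to change.** In SAP section 8.7.2, item B, change the creatinine unit in the eGFR formula from mmol per L to µmol per L and keep 88.4. Keeping mmol/L and changing the divisor to 0.0884 is equivalent, but µmol/L matches Protocol Table 5-3.

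Check the program against one hand-worked case: a man aged 60, race factor 1, with creatinine 88.4 µmol/L should give 81.0. Confirm that the unit in the analysis dataset is the one the formula expects.

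The cost is one word and a short programming check. SAP section 4.8 already provides for minor corrections by addendum, so no protocol amendment is needed.
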